##### *Newly Diagnosed Multiple Myeloma (C16005):*

In Study C16005, ixazomib is given weekly (Days 1, 8, and 15), in combination with lenalidomide (Days 1-21), and dexamethasone (Days 1, 8, 15, and 22) in a 28-day cycle. Patients with newly diagnosed MM were enrolled and treated with oral ixazomib (days 1, 8, and 15) plus lenalidomide 25 mg (days 1-21) and dexamethasone 40 mg (days 1, 8, 15, 22) for up to twelve 28-day cycles, then maintenance therapy with ixazomib (same schedule) every 28 days until progression. Patients were allowed to undergo stem cell collection after 3 cycles and discontinue for autologous stem cell transplant (ASCT).

after 6 cycles. Overall, 65 patients were enrolled, 15 in Phase 1 and 50 in Phase 2. Patients received a median of 6 cycles (range 1-19) with 27 (42%) remaining on treatment as of November 2012. Of those who have undergone stem cell mobilization, a median yield was  $11.3 \times 10^6$  CD34+ cells/Kg (range 5-28). Ixazomib MTD was established as 2.97 mg/m^2 and RP2D was selected as 2.23 mg/m^2; RP2D translates to a 4 mg fixed dose based on population PK results. Among the 64 evaluable patients, the overall response rate was 92%, including 55% VGPR and 23% CR. Median time to first response was 0.92 months (range 0.89-6.44).

*Relapsed Multiple Myeloma (Tourmaline MM01):* This international phase 3 trial enrolled adults with RRMM who had received 1-3 prior lines of therapy and who were not refractory to prior lenalidomide or PI-based therapy. Patients were randomized 1:1 to receive ixazomib 4 mg or matching placebo weekly on d 1, 8, and 15, plus lenalidomide 25 mg PO on d 1-21 and dexamethasone 40 mg PO on d 1, 8, 15, and 22, in 28-day cycles. 722 patients were randomized (360 IRd; 362 Rd); 19% had high-risk cytogenetics by FISH (del(17), t(4;14), or t(14;16)), including 10% del(17). The study demonstrated significantly better PFS with IRd (20.6 months) compared with Rd (14.7 months); a 35% improvement in PFS (HR 0.742; p=0.012). The PFS improvement was seen in all patient subgroups, especially in patients with del17p, where the improvement with the combination was quite striking.

#### **Potential Risks and Benefits of ixazomib:**

Please refer to the current ixazomib Investigator's Brochure (IB).

#### 1.5

##### Pembrolizumab:

The importance of intact immune surveillance in controlling outgrowth of neoplastic transformation has been known for decades. Accumulating evidence shows a correlation between tumor-infiltrating lymphocytes (TILs) in cancer tissue and favorable prognosis in various malignancies. In particular, the presence of CD8+ T-cells and the ratio of CD8+ effector T-cells / FoxP3+ regulatory T-cells seems to correlate with improved prognosis and long-term survival in many solid tumors.

The PD-1 receptor-ligand interaction is a major pathway hijacked by tumors to suppress immune control. The normal function of PD-1, expressed on the cell surface of activated T-cells under healthy conditions, is to down-modulate unwanted or excessive immune responses, including autoimmune reactions. PD-1 (encoded by the gene Pdcd1) is an Ig superfamily member related to CD28 and CTLA-4, which has been shown to negatively regulate antigen receptor signaling upon engagement of its ligands (PD-L1 and/or PD-L2). The structure of murine PD-1 has been resolved. PD-1 and family members are type I transmembrane glycoproteins containing an Ig Variable-type (V-type) domain responsible for ligand binding and a cytoplasmic tail which is responsible for the binding of signaling molecules. The cytoplasmic tail of PD-1 contains 2 tyrosine-based signaling motifs, an immunoreceptor tyrosine-based inhibition motif (ITIM) and an immunoreceptor tyrosine-based switch motif (ITSM). Following T-cell stimulation, PD-1 recruits the tyrosine phosphatases SHP-1 and SHP-2 to the ITSM motif within its cytoplasmic tail, leading to the dephosphorylation of effector molecules such as CD3 $\zeta$ , PKC $\theta$  and ZAP70 which are involved in the CD3 T-cell signaling cascade. The mechanism by which PD-1 down modulates T-cell responses is similar to, but distinct from that of CTLA-4 as both molecules regulate an overlapping set of signaling proteins. PD-1 was shown to be expressed on activated lymphocytes including peripheral CD4+ and CD8+ T-cells, B-cells, Tregs and Natural Killer cells. Expression has also been

shown during thymic development on CD4-CD8- (double negative) T-cells as well as subsets of macrophages and dendritic cells. The ligands for PD-1 (PD-L1 and PD-L2) are constitutively expressed or can be induced in a variety of cell types, including non-hematopoietic tissues as well as in various tumors. Both ligands are type I transmembrane receptors containing both IgV- and IgC-like domains in the extracellular region and contain short cytoplasmic regions with no known signaling motifs. Binding of either PD-1 ligand to PD-1 inhibits T-cell activation triggered through the T-cell receptor. PD-L1 is expressed at low levels on various non-hematopoietic tissues, most notably on vascular endothelium, whereas PD-L2 protein is only detectably expressed on antigen-presenting cells found in lymphoid tissue or chronic inflammatory environments. PD-L2 is thought to control immune T-cell activation in lymphoid organs, whereas PD-L1 serves to dampen unwarranted T-cell function in peripheral tissues. Although healthy organs express little (if any) PD-L1, a variety of cancers were demonstrated to express abundant levels of this T-cell inhibitor. PD-1 has been suggested to regulate tumor-specific T-cell expansion in subjects with melanoma (MEL). This suggests that the PD-1/PD-L1 pathway plays a critical role in tumor immune evasion and should be considered as an attractive target for therapeutic intervention.

Pembrolizumab is a potent and highly selective humanized monoclonal antibody (mAb) of the IgG4/kappa isotype designed to directly block the interaction between PD-1 and its ligands, PD-L1 and PD-L2. Keytruda® (pembrolizumab) has recently been approved in the United States for the treatment of patients with unresectable or metastatic melanoma and disease progression following ipilimumab and, if BRAF V600 mutation positive, a BRAF inhibitor.

An open-label Phase I trial (Protocol 001) is being conducted to evaluate the safety and clinical activity of single agent MK-3475. The dose escalation portion of this trial evaluated three dose levels, 1 mg/kg, 3 mg/kg, and 10 mg/kg, administered every 2 weeks (Q2W) in subjects with advanced solid tumors. All three dose levels were well tolerated and no dose-limiting toxicities were observed. This first in human study of MK-3475 showed evidence of target engagement and objective evidence of tumor size reduction at all dose levels (1 mg/kg, 3 mg/kg and 10 mg/kg Q2W). No MTD has been identified to date. 10 mg/kg Q2W, the highest dose tested in PN001, will be the dose and schedule utilized in Cohorts A, B, C and D of this protocol to test for initial tumor activity. Recent data from other clinical studies within the MK-3475 program has shown that a lower dose of MK-3475 and a less frequent schedule may be sufficient for target engagement and clinical activity.

PK data analysis of MK-3475 administered Q2W and Q3W showed slow systemic clearance, limited volume of distribution, and a long half-life (refer to IB). Pharmacodynamic data (IL-2 release assay) suggested that peripheral target engagement is durable (>21 days). This early PK and pharmacodynamic data provides scientific rationale for testing a Q2W and Q3W dosing schedule.

A population pharmacokinetic analysis has been performed using serum concentration time data from 476 patients. Within the resulting population PK model, clearance and volume parameters of MK-3475 were found to be dependent on body weight. The relationship between clearance and body weight, with an allometric exponent of 0.59, is within the range observed for other antibodies and would support both body weight normalized dosing or a fixed dose across all body weights. MK-3475 has been found to have a wide therapeutic range based on the melanoma indication. The differences in exposure for a 200 mg fixed dose regimen relative to a 2 mg/kg Q3W body weight based regimen are anticipated to remain well within the established exposure margins of 0.5 –

[figure not shown]
5.0 for MK-3475 in the melanoma indication. The exposure margins are based on the notion of similar efficacy and safety in melanoma at 10 mg/kg Q3W vs. the proposed dose regimen of 2 mg/kg Q3W (i.e. 5-fold higher dose and exposure). The population PK evaluation revealed that there was no significant impact of tumor burden on exposure. In addition, exposure was similar between the NSCLC and melanoma indications. Therefore, there are no anticipated changes in exposure between different indication settings.

The rationale for further exploration of 2 mg/kg and comparable doses of pembrolizumab in solid tumors is based on: 1) similar efficacy and safety of pembrolizumab when dosed at either 2 mg/kg or 10 mg/kg Q3W in melanoma patients, 2) the flat exposure-response relationships of pembrolizumab for both efficacy and safety in the dose ranges of 2 mg/kg Q3W to 10 mg/kg Q3W, 3) the lack of effect of tumor burden or indication on distribution behavior of pembrolizumab (as assessed by the population PK model) and 4) the assumption that the dynamics of pembrolizumab target engagement will not vary meaningfully with tumor type.

The choice of the 200 mg Q3W as an appropriate dose for the switch to fixed dosing is based on simulations performed using the population PK model of pembrolizumab showing that the fixed dose of 200 mg every 3 weeks will provide exposures that 1) are optimally consistent with those obtained with the 2 mg/kg dose every 3 weeks, 2) will maintain individual patient exposures in the exposure range established in melanoma as associated with maximal efficacy response and 3) will maintain individual patients exposure in the exposure range established in melanoma that are well tolerated and safe.

A fixed dose regimen will simplify the dosing regimen to be more convenient for physicians and to reduce potential for dosing errors. A fixed dosing scheme will also reduce complexity in the logistical chain at treatment facilities and reduce wastage.

**Pembrolizumab experience in multiple myeloma:** The keynote-23 trial enrolled patients with RRMM who have failed  $\geq 2$  prior therapies including a proteasome inhibitor and an IMiD. During the dose determination phase, cohorts of 3-6 patients were enrolled at 2 mg/kg of pembrolizumab every 2 weeks (Q2W) in combination with 10 mg or 25 mg of lenalidomide on days 1-21 and 40 mg low-dose dexamethasone weekly, to be repeated every 28 days. After an MTD was identified, additional patients were enrolled at a fixed dose of 200 mg of pembrolizumab in combination with lenalidomide and dexamethasone. Overall, 51 patients with a median of 4 prior lines of therapy were enrolled, 78% of who were refractory to the last line of therapy. Most common AEs noted included cytopenias, fatigue and gastrointestinal side effects. DLTs seen included tumor lysis, neutropenia and pneumonia. Overall response rate was 50% including 16% with VGPR or better; the corresponding numbers were 38% and 13% among the patients who were refractory to lenalidomide.

Data cutoff date: September 22, 2015

18

In a similar phase II study, 24 patients with RRMM received 28-day cycles of pembrolizumab (at a dose of 200 mg IV) every 2 weeks (in a run off phase, first 6 patients received 200 mg IV every 4 weeks) plus pomalidomide (4 mg daily x 21 days) and dexamethasone 40 mg weekly. Patients with relapsed and/or refractory myeloma with two or more lines of prior therapy that included an IMid and a proteasome inhibitor were eligible for this trial. Thirty-three patients, most refractory to proteasome inhibitors and IMiDs (70% double refractory), were enrolled. The overall response rate was 60% among the 27 patients evaluable for response, including 5 patients with a VGPR or better.

#### 1.6 Rationale for the current trial:

Currently, there is considerable amount of work is being done to enhance this regimen. Binding of the PD-1 ligands, PD-L1 and PD-L2, to the PD-1 receptor found on T cells, inhibits T cell proliferation and cytokine production. Up regulation of PD-1 ligands occur in some tumors and signaling through this pathway can contribute to inhibition of active T-cell immune surveillance of tumors. Pembrolizumab is a monoclonal antibody that binds to the PD-1 receptor and blocks its interaction with PD-L1 and PD-L2, releasing PD-1 pathway-mediated inhibition of the immune response, including the anti-tumor immune response. In syngeneic mouse tumor models, blocking PD-1 activity resulted in decreased tumor growth. In the setting of myeloma, B-cell responses are altered to a state of functional hypogammaglobulinemia, leading to an increased risk for infections. T-cell-mediated immunity is also severely impaired in MM with T-helper (Th)1/Th2 imbalance leading to immune dysfunction. Several studies have shown that PD-L1 is absent from normal plasma cells, whereas it is expressed on myeloma cell lines and primary myeloma tumor cells from patients with MM. It has been demonstrated that PD-1 expression is up regulated on T cells isolated from patients with MM, suggesting that this pathway is of importance in mediating the immunosuppressive state in this patient population. Benson et al. have shown that NK cells from MM patients express PD-1 and suggested that PD-1/PD-L1 interactions undermine the immunological control of MM by NK cells. They have also demonstrated that the application of an anti-PD-1 monoclonal antibody enhances the cytolytic activity of NK cells against autologous, primary MM cells. Preliminary results from ongoing trials of pembrolizumab with lenalidomide or pomalidomide have demonstrated evidence of activity. Ixazomib has excellent activity in MM, and proteasome inhibitors have been shown to be active in combination with other immunotherapy approaches such as elotuzumab and daratumumab. Given these findings, it is rational to evaluate the combination of pembrolizumab in combination with ixazomib and dexamethasone in relapsed myeloma.

**2.0 Goals****2.1 Primary**

To determine the overall response rate ( $\geq$ PR) of pembrolizumab in combination with standard doses of ixazomib and dexamethasone, in patients with relapsed symptomatic MM.

**2.2 Secondary**

- 2.21 To determine the  $\geq$  very good partial response (VGPR) and complete response (CR) rate of pembrolizumab added to standard doses of ixazomib and dexamethasone in relapsed myeloma.
- 2.22 To determine the progression free survival and overall survival among patients with relapsed MM following treatment with the combination of pembrolizumab, ixazomib and dexamethasone.
- 2.23 To determine the toxicities associated with pembrolizumab added to standard doses of ixazomib and dexamethasone in patients with relapsed MM.

**2.3 Correlative Research**

- 2.31 PDL-1 expression on myeloma cells and non-tumor cell compartments from the bone marrow will be assessed at baseline
- 2.32 Measures of T-cell activation / exhaustion will be assessed at baseline and after Cycle 1 and Cycle 3.
- 2.33 NK cell function and numbers will be evaluated at baseline and after Cycle 1 and Cycle 3.

**3.0 Patient Eligibility****3.1 Inclusion Criteria**

3.11 Diagnosis of relapsed, symptomatic multiple myeloma by IMWG diagnostic criteria for multiple myeloma.

3.12 Age  $\geq$ 18 years

3.13 The following laboratory values obtained  $\leq$ 14 days prior to registration.

- Calculated creatinine clearance (using Cockcroft-Gault equation below)\*  $\geq$ 30 mL/min
- Absolute neutrophil count (ANC)  $\geq$ 1000/mm^3
- Platelet count  $\geq$ 75000/mm^3 Note: Platelet transfusion is not allowed  $\leq$ 3 days prior to registration.
- Hemoglobin  $\geq$ 8.0 g/dL
- Total bilirubin  $\leq$  1.5 x ULN
- ALT and AST  $\leq$  2.5 x ULN

\*Cockcroft-Gault Equation:

Creatinine clearance for males =  $(140 - \text{age})(\text{actual body weight in kg}) / (72)(\text{serum creatinine in mg/dL})$

Creatinine clearance for females =  $(140 - \text{age})(\text{actual body weight in kg})(0.85) / (72)(\text{serum creatinine in mg/dL})$

3.14 Must have relapsed or refractory disease after treatments including three therapies: proteasome inhibitors, IMiDS, and anti-CD38 antibody.

3.15 Measurable disease of multiple myeloma as defined by at least ONE of the following:

- Serum monoclonal protein  $\geq 1.0$  g/dL (see Section 11.1 for definition)
- $\geq 200$  mg of monoclonal protein in the urine on 24 hour electrophoresis
- Serum immunoglobulin free light chain  $\geq 10$  mg/dL AND abnormal serum immunoglobulin kappa to lambda free light chain ratio.

3.16 ECOG performance status (PS) 0, or 1 (Appendix I).

3.17 Provide informed written consent.

3.18 Negative pregnancy test done  $\leq 7$  days prior to registration, for women of childbearing potential only.

3.19a Willing to follow strict birth control measures as detailed in Section 9.9i.

Female patients: If they are of childbearing potential, agree to one of the following:

- Practice 2 effective methods of contraception, at the same time, from the time of signing the informed consent form through 120 days after the last dose of study drug, AND must also adhere to the guidelines of any treatment-specific pregnancy prevention program, if applicable, OR
- Agree to practice true abstinence when this is in line with the preferred and usual lifestyle of the subject. (Periodic abstinence [eg, calendar, ovulation, symptothermal, post-ovulation methods] and withdrawal are not acceptable methods of contraception.)

Male patients: even if surgically sterilized (i.e., status post-vasectomy), must agree to one of the following:

- Agree to practice effective barrier contraception during the entire study treatment period and through 120 days after the last dose of study drug, OR
- Must also adhere to the guidelines of any treatment-specific pregnancy prevention program, if applicable, OR
- Agree to practice true abstinence when this is in line with the preferred and usual lifestyle of the subject. (Periodic abstinence (eg, calendar, ovulation, symptothermal, post-ovulation methods] and withdrawal are not acceptable methods of contraception.)

3.19b Willing to return to enrolling institution for follow-up (during the Active Monitoring Phase of the study).

3.19c Willing to provide bone marrow and blood samples for planned research (see Sec. 14.1).

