- 5) Collected prior to C1D1 treatment; at the end of 2 cycles, and to document progression or CR at any time point.
- 6) The diary must begin the day the patient starts taking the medication and must be completed per protocol and returned to the treating institution.
- 7) Affected immunoglobulin refers to the baseline M-protein type, that is, IgG, IgA, IgD, or IgM. Not applicable if patient “non-secretory” or if patient has no heavy chain, i.e. light chain myeloma.
- 8) Collected prior to C1D1 and C1D22; then every cycle prior to D1 treatment; and to document progression or CR at any timepoint.
- 9) The following testing may be done if clinically indicated: Myeloma FISH, plasma cell proliferation, and flow cytometry (MRD)
- 10) Does not need to be repeated at Cycle 1 Day 1. Baseline values can be used for Cycle 1.
- 11) If patient is stable after 2 cycles, physical exam can be decreased to Weeks 1 and 7 of each cycle.
- 12) Only if clinically indicated for MRD negative patients every 12 weeks.
- 13) Urine Electrophoresis required only if used to assess disease response.

R) Research funded (see Section 19.0). Will be charged to study and not to patient's account.

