**6.13 Prior to accepting the registration, registration/randomization application will verify the following:**

- IRB approval at the registering institution
- Patient eligibility
- Existence of a signed consent form
- Existence of a signed authorization for use and disclosure of protected health information

**6.14 Documentation of IRB approval must be on file in the Registration Office before an investigator may register any patients.**

In addition to submitting initial IRB approval documents, ongoing IRB approval documentation must be on file (no less than annually) at the Registration Office [REDACTED] If the necessary documentation is not submitted in advance

of attempting patient registration, the registration will not be accepted and the patient may not be enrolled in the protocol until the situation is resolved.

When the study has been permanently closed to patient enrollment, submission of annual IRB approvals to the Registration Office is no longer necessary.

- 6.15 At the time of registration, the following will be recorded:
  - Patient has/not given permission to store and use his/her sample(s) for future research of Multiple Myeloma at Mayo.
  - Patient has/not given permission to store and use his/her sample(s) for future research to learn, prevent, or treat other health problems.
  - Patient has/not given permission for MCCC to give his/her sample(s) to researchers at other institutions.
- 6.16 Treatment on this protocol must commence at a Mayo Clinic Institution, under the supervision of a hematologist.
- 6.17 Treatment cannot begin prior to registration and must begin ≤ 14 days after registration.
- 6.18 Pretreatment tests/procedures (see Section 4.0) must be completed within the guidelines specified on the test schedule.
- 6.19 All required baseline symptoms (see Section 10.61) must be documented and graded.
- 6.19a Blood draw kit is available on site, if applicable (see Section 14).

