### 8.11 Instruction for initiation of a new cycle of therapy

A new cycle of treatment may begin on the scheduled Day 1 of a new cycle if:

- The ANC is  $\geq 1000/\mu\text{L}$
- The platelet count is  $\geq 75,000/\mu\text{L}$
- Any other non-hematologic drug-related (possible, probable, or definite) adverse event that may have occurred has resolved to  $\leq$ Grade 1 or baseline severity.

If these conditions are not met on Day 1 of a new cycle, dosing should be delayed for 1 week. At the end of that time, the patient should be re-evaluated to determine whether the criteria have been met. If the patient continues to fail to meet the above-cited criteria, delay therapy and continue to re-evaluate.

If any drug dosing was halted during the previous cycle and was restarted with a one-level dose reduction without requiring an interruption for the remainder of the cycle, then that reduced dose level will be initiated on Day 1 of the new cycle.

If any drug dosing was omitted for the remainder of the previous cycle or if the new cycle is held due to known hematologic toxicity newly encountered on the scheduled Day 1, then the new cycle will be started with a one-level dose reduction. If a new cycle of therapy cannot be restarted within 4 weeks of the scheduled Day 1 due to non-resolution of drug related toxicities, the patient will be removed from protocol therapy and will go to event monitoring.

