### **9.2 Disallowed concurrent treatment**

The following treatments are not permitted during the trial:

- Any other investigational treatment
- Any other systemic anti-neoplastic therapy including, but not limited to, immunotherapy, hormonal therapy or monoclonal antibody therapy.
- Any external beam radiotherapy
- Platelet transfusions to help patients meet eligibility criteria are not allowed within 3 days prior to study drug dosing for any dosing day

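### The platelet-transfusion ban in Section 3.13 runs from registration, not from the qualifying blood sample, so a recently transfused count can meet the threshold and stand for Cycle 1 Day 1

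*Combined protocol and SAP*

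**What the plan says.** Five provisions of the protocol bear on this point.

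- **Section 3.13** opens with "The following laboratory values obtained" and sets a window of 14 days before registration. Its platelet item requires at least 75,000/mm³ and adds the note "Platelet transfusion is not allowed", with the limit given as "3 days prior to registration".
- **Section 9.2** lists among disallowed treatments: "Platelet transfusions to help patients meet eligibility criteria are not allowed within 3 days prior to study drug dosing for any dosing day".
- **Section 4.1, footnote 10**, attached to the CBC and the chemistry group in the Day 1 column, reads: "Does not need to be repeated at Cycle 1 Day 1. Baseline values can be used for Cycle 1".
- **Section 6.17** states "Treatment cannot begin prior to registration and must begin" no later than 14 days after registration.
- **Section 8.11** introduces its count criteria with "A new cycle of treatment may begin on the scheduled Day 1 of a new cycle if". The platelet criterion is again 75,000, and no transfusion condition is attached.

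No provision requires the qualifying platelet count itself to be free of recent transfusion.

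**The concern.** The note in 3.13, read with 9.2, has a clear purpose: the platelet threshold should be met by the patient's own count, not by transfused platelets. A transfusion affects the sample drawn after it. The protective interval therefore has to be counted back from the sample. Counted back from registration, it protects only samples drawn close to registration, while the protocol allows samples from two weeks before.

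Footnote 10 carries the same number forward. If the baseline count is reused, nothing in the schedule requires a fresh count before the first dose, so the first dose can rest on an old and possibly transfusion-supported value.

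Three things are at stake:

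- whether the eligibility criterion does what it was written to do;
- whether the baseline platelet grade, which Section 10.61 asks sites to record, is the patient's own;
- how readily a Grade 4 platelet decrease lasting more than 7 days, which is a DLT under Section 16.4, can be attributed if it occurs in one of the first 6 patients.

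**Working it through.** The plan states no figure on this point, so the check is a comparison of date windows. Take registration as day 0, a transfusion on day T, the qualifying count on day C and the first dose on day D.

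**Inputs**

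- C lies between −14 and 0 (3.13).
- T may not lie between −3 and 0 (3.13).
- D lies between 0 and 14 (6.17).
- D − T may not lie between 0 and 3 (9.2).
- The baseline count may be reused on day D (4.1, footnote 10).

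**Step 1: interval guaranteed before the count.** Let the count be drawn on day −k. The latest permitted transfusion at or before it is on day −4 when k is 3 or less, and on day −k itself when k is 4 or more. The smallest permitted gap is therefore max(0, 4 − k) days.

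| Draw day | Smallest permitted gap from transfusion to count |
|---|---|
| 0 | 4 days |
| −1 | 3 days |
| −2 | 2 days |
| −3 | 1 day |
| −4 to −14 | 0 days |

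**Step 2: does 9.2 close the gap?** A transfusion that 3.13 permits before a qualifying count has T ≤ −4. The first dose has D ≥ 0. Hence D − T ≥ 4, which is always outside the 3-day window of 9.2.

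**Step 3: enumeration.** The documents do not say how long a transfusion supports a count. As an assumption, borrow their own interval and call a count supported if 0 ≤ C − T ≤ 3.

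- Draw days −14 to −4: 11 days × 4 transfusion days = 44 pairs.
- Draw days −3, −2 and −1: 3 + 2 + 1 = 6 pairs.
- Draw day 0: none.
- Total: 50 pairs × 15 possible first-dose days = 750 permitted sequences.

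Adding 9.2 leaves 750. Counting the same 3 days back from the sample leaves 0. That last result follows from the definition used, so it illustrates the anchoring and is no argument for any particular interval.

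**Step 4: age of a reused count.** The maximum is 14 days (3.13) + 14 days (6.17) = 28 days at first dose.

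**Example.** Transfusion on day −10, count at or above 75,000 on day −9, registration on day 0, first dose on day 14. The 3.13 ban covers days −3 to 0 and the 9.2 ban covers days 11 to 14, so neither is breached. The reused count is 14 + 9 = 23 days old at first dose.

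**Side check on the primary test.** Exact binomial calculation of the design in Section 16.2 (stop at 4 or fewer of 14; promising at 15 or more of 37) gives a significance level of 0.0954 and power of 0.8526, against the stated .095 and 0.853. These depend only on the cut-offs, the patient numbers and the assumed success proportions. The transfusion wording does not enter.

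**The case against.** The strongest reply is that the protocol has other protection.

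- Section 4.1 schedules a CBC weekly in the first cycle.
- Section 8.3 acts on platelets below 30 × 10⁹/L from Day 2.
- Footnote 10 permits reuse but does not forbid a fresh Day 1 count.
- Section 3.29f lets the investigator exclude a patient whose therapy or laboratory findings might confound the results.
- Most timed criteria in Section 3 run from registration, so the anchor follows the document's own convention.

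Much of this stands, and it keeps the point small. Reliance on a stale or supported count should be short, essentially the first dose. It does not remove the gap. The weekly counts that follow Day 1 come after dosing has begun, 8.3 does not respond to values between 30 and 75 × 10⁹/L, and 3.29f is discretionary. The protocol also departs from its convention where it wants assurance at dosing: footnote 3 times the pregnancy test both from registration and from the first dose.

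Stronger readings are tempting, and the documents do not support them.

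- **A reader might infer that one such patient supplies half of the 2-of-6 trigger in 16.4 for a reason unrelated to the regimen.** Section 16.4 counts only events judged at least possibly related to treatment, and its consequence is a continued temporary halt while dosing is reviewed. Attribution may become harder, but a DLT is not thereby counted. The stopping rule in 16.52 concerns non-hematologic events only.
- **A reader might take the share of draw days without protection as a frequency.** It counts calendar days, not patients.
- **A reader might cite the 43% drug-related thrombocytopenia in the single-agent ixazomib study (Section 1.4).** That figure says nothing about transfusion-supported counts at entry.
- **A reader might set 28 days against the ±4 days of the Day 1 column.** One is the age of a laboratory value and the other a visit window, so the comparison shows only that the two provisions need reconciling.

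**Conclusion.** The point holds in limited form. The transfusion bans in 3.13 and 9.2 run from registration and from dosing, and neither is tied to the qualifying sample. A count drawn soon after a transfusion on day −4 or earlier can meet the 75,000 threshold. Footnote 10 with 6.17 then lets it stand for Cycle 1 Day 1 at an age of up to 28 days.

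The gap in the dates follows from the text without further assumption. Calling a particular count transfusion-supported does rest on an assumption about how long the effect lasts, which the documents do not give. Nor do they say how many candidates are transfused in the two weeks before registration, so no expected number of patients can be stated.

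The consequences are confined to eligibility, baseline platelet grade and the attribution of a platelet DLT among the first 6 patients. Significance level, power and sample size are unaffected. This is a cheap improvement, not a defect that threatens the trial's conclusion.

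**What to change.** Reconcile Section 3.13, Section 9.2 and footnote 10 of Section 4.1 so that the protocol's existing transfusion window runs from the platelet count used for eligibility, and equally from any count used for Cycle 1 Day 1. The second part is needed because 8.11 carries no transfusion condition. A repeat count drawn 4 days before dosing and shortly after a transfusion would pass both 8.11 and 9.2.

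Separately, reconcile footnote 10 with the Day 1 window of Section 4.1 and the platelet criterion of 8.11, and state how old a reused baseline count may be.

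The length of the interval, the permitted age and any criterion for starting treatment are clinical decisions for the sponsor. This point asks only that the sections agree on the date from which the window runs.

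The cost is a few wording changes, one more routine blood draw for some patients, and the loss of a few candidates whose qualifying count was transfusion-supported, which is the group that the note in 3.13 appears meant to exclude.
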